13.4.6 Descriptive Analyses

Demographic, patient characteristics, medication use and study completion status will be summarized for the two treatment groups using mean \pm standard deviation or median [interquartile range] for continuous variables and frequency and percentages for categorical variables. Treatment comparisons will be performed using the two-sample t-test or Wilcoxon Rank sum test for continuous variables and the Fisher's Exact test for categorical variables. All tests will be conducted at $\alpha=0.05$

Additionally, we may perform some exploratory analyses when the two groups in Phase 2 become substantially imbalanced in their demographics and disease characteristics. Also, we will perform comparisons the groups who choose to continue on Phase 2 and those who opt out, in both arms. Any apparent difference will be noted.

13.5 Interim Analyses

No interim for efficacy nor futility analyses are planned for this study.

Interim data summaries will be provided to the DSMB in accordance with the DSMB charter. Data presentation by study arm will be provided in a blinded fashion with no indication of actual treatment assignment, unless specifically requested by the DSMB to facilitate their review.

13.5.1 Interim Analysis of Efficacy Data

N/A

13.5.2 Interim Analysis of Safety Data

N/A

13.5.3 Futility Analysis

N/A

13.5.4 Statistical Hypotheses

See above

13.6 Sample Size Considerations

The sample size was based on the primary endpoint of the percent of patients in histologic remission (<15 eosinophils/hpf) at the end of Phase 1. Based on preliminary data, it is assumed that the remission rate for the 1FED population is 45%.¹⁶ We assume that the remission rate in the 6FED population will be increased to 70%. A sample size of 60 patients per group (120 total patients) will provide at least 80% power to detect a difference in rates between groups of 25% at the two-sided $\alpha=0.05$. This calculation is based on a likelihood ratio test statistic for comparing proportions. To allow for a potential approximate 15% drop-out, the sample size will be increased to 68 patients per group (136 total patients). This calculation was performed using the PASS vers. 12 software. The following table displays the robustness of the sample size under various response rate and drop-out rate scenarios.

Sample Size per group	Difference to detect with 80% power if 1FED rate is 45%	Difference to detect with 80% power if 1FED rate is 50%	Difference to detect with 80% power if 1FED rate is 55%
56	26%	24%	24%
60	25%	23.5%	23.5%
64	24%	23%	23%
68	24%	23%	22%

14.IDENTIFICATION AND ACCESS TO SOURCE DATA

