4. STUDY DESIGN

4.1 Description of Study Design

We will be recruiting a total of 136 participants, between the ages of 18-60. Participants will be enrolled in this study based on the presence of active eosinophilic esophagitis and adherence to the inclusion and exclusion criteria.

[figure not shown]
We intend to conduct a prospective non-blinded randomized trial that compares a 1-food elimination diet (1FED) versus a 6-food elimination diet (6FED) for six weeks (Phase 1). Subsequently, non-responders to 1FED dietary elimination therapy will be treated with 6FED and non-responders to 6FED will be treated with SGC (swallowed fluticasone at a dose of 880 mcg twice a day) for six weeks (Phase 2) while on an unrestricted diet, if the participant chooses to continue in to Phase 2. The empiric dietary therapy interventions are as follows: 1-food elimination diet (1FED)—avoidance of milk vs. 6-food elimination diet (6FED)—avoidance of milk, egg, wheat, soy, fish/shellfish, and peanut/tree nuts, for six weeks. Milk elimination for both 1FED and 6FED includes all mammal milk (i.e. goat, sheep, and cow's milk must all be eliminated). The study design is shown schematically in Figure 1 Study Design Flowchart.

In Phase 1, all participants will be randomized 1:1 to either 1 food elimination (milk elimination alone, 1FED) or 6 food elimination (milk, egg, wheat, soy, fish/shellfish, peanut/tree nuts elimination, 6FED) therapeutic diet. At the end of this phase, an EGD will be performed to assess remission. Attainment of remission (esophageal eosinophil counts <15 eosinophils/high powered field) after Phase 1 will result in study discontinuation and maintenance of the “successful” dietary therapy. Treatment non-responders may choose whether or not to continue into Phase 2. Dietary therapy non-responders who were on 6FED in Phase 1 and continue in to Phase 2 will receive topical swallowed steroids for six weeks (Phase 2) followed by EGD with esophageal biopsies. These participants will return to an unrestricted diet (i.e. stop 6FED) prior to beginning topical swallowed steroid therapy. Dietary non-responders in Phase 1 who were on 1FED and continue in to Phase 2 will continue to a 6FED therapeutic diet (Phase 2) for six weeks followed by EGD with esophageal biopsies to assess remission.

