9.4 End of 1st Treatment phase or Early Withdrawal (Week 6)

For participants who have completed the 6 week Phase 1 or have withdrawn early from the study, the following procedures will occur:

- Measure vitals (blood pressure, heart rate, respiratory rate, temperature), height and weight
- Physical exam performed by a study clinician or qualified staff member
- Collect stool sample (if possible) from subjects who have consented to stool collection
- Administer patient reported outcome questionnaires
- Assess AEs
- Obtain up to 4 biopsies from the esophagus for research purposes (taken during SOC EGD)
 - One of these esophageal biopsies will be used for EDP
- Research lab samples
 - Blood serum (~1-2 tsp, or 5-10 mL) for food IgE, CRD, and IgG4
 - Blood serum (~3-6 tsp, or 15-30 mL) for T cell studies
 - Blood (6-10 mL) or saliva (1-2 mL) for future genetic testing may be collected at this visit (if not collected previously)
 - Blood for metabolomics (1 tsp, or 3-5 mL)
 - CBC with differential - if a CBC with differential was obtained clinically as part of standard of

care, obtain the results from the standard of care CBC

- Assess participant compliance with diet therapy and concomitant medications
- Pregnancy Test (urine)

Stool samples may be collected from participants who have consented to stool collection. Stool will only be collected at some, but not all, participating centers.

If a participant withdraws from the study before completing 6 weeks of dietary therapy, the end of treatment/early withdrawal visit should be conducted within one week of the participant's stopping dietary therapy. Participants should stay on their dietary therapy until results of biopsies are communicated to them.

Those participants who have resolution of their inflammation on endoscopy at the end of Phase 1 will complete the study at this time. Subjects with continued active inflammation will move on to phase 2, 6FED non-responders will start treatment with swallowed SGC (880mcg BID fluticasone propionate) and unrestricted diet and 1FED non-responders will start treatment of 6FED.

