11.3 Participant Replacement

Enrolled participants who start on the initial dietary protocol and prematurely discontinue/withdraw from the study will be replaced if they do not reach Week 6 of the study including the EGD. Additional participants will be enrolled in the same manner as all other participants. Participant numbers will not be re-used. Any enrolled participant will be included into any intent to treat analysis.

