13.4 Analysis Plan

13.4.1 Analysis Populations

The analysis population for the primary and key secondary endpoints will be the intent-to-treat population. All patients that have been randomized will be included in this analysis. Patients for which the primary endpoint of histological remission cannot be determined will be imputed as treatment failures.

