The instructions for the 1FED and 6FED therapeutic diets will be standardized across sites by providing consensus documents produced by registered dietitians who are experts in dietary elimination in EoE. There are currently no validated dietary questionnaires for measuring food allergen intake in adults in the US. Dietary intake and *consumption* of the allergens will be measured at the start of the trial and adherence to the dietary elimination (i.e. *avoidance* of the allergens) during the trial will be measured using modified versions of the NCI's usual dietary intake/diet history questionnaires and 3-day food diaries (<http://cancercontrol.cancer.gov>). Stool samples may be collected from subjects who consent to stool collection to evaluate the effect of diet on the microbiome.

Similarly, standardized instructions for using SGC will be provided, based on our prior studies. We have chosen to use fluticasone propionate (FP) rather than budesonide in this study, given our prior work in this area, and our recent finding that high-dose fluticasone is well tolerated and highly effective, and our preliminary findings concerning esophageal transcripts that predict responsiveness to FP therapy. The study design is shown schematically in Figure 1 Study Design Flowchart.

Figure 1 Study Design Flowchart

Analysis Populations

The analysis population for the primary and secondary endpoints will be the intent-to-treat population with the goal of including patients who have been randomized in the analyses. However, we will exclude patients who were inappropriately randomized and never completed the enrollment visit. Patients for which the primary endpoint of histological remission cannot be determined will be imputed as treatment failures. To maximize comparability with other studies, we will also perform per protocol analyses, including only individuals who complete the study phase of interest for all proposed studies.

Variables of Interest

Primary outcome:

- 1) Remission rate (<15 peak eosinophils/hpf)

Secondary outcomes:

- 1) Change in eosinophils/hpf from baseline to post treatment
- 2) Remission status: Patients will be classified into 3 remission categories: complete histological remission (≤ 1 peak eosinophils/hpf); partial remission (2-14 peak eosinophils/hpf); no remission (≥ 15 peak eosinophils/hpf)

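### The drop-out allowance in section 13.6 does not match the failure rule for missing endpoints: with 68 randomised per arm, power is about 80%, 75% and 70% at 5%, 10% and 15% missing

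*Protocol*

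**What the plan says.** Protocol 13.6 assumes remission of 45% on 1FED and 70% on 6FED and states that 60 per group give at least 80% power at two-sided 5%, using a likelihood-ratio test for two proportions. It then says: "To allow for a potential approximate 15% drop-out, the sample size will be increased to 68 patients per group (136 total patients". The two rates and the 25-point difference are not altered. A table follows, introduced with "The following table displays the robustness of the sample size under various response rate and drop-out rate scenarios".

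The primary analysis is intention-to-treat. Protocol 13.4.1 includes every randomised patient and adds: "Patients for which the primary endpoint of histological remission cannot be determined will be imputed as treatment failures". The SAP (Analysis Populations) repeats that rule. Its only exclusion is narrow: "we will exclude patients who were inappropriately randomized and never completed the enrollment visit". Complete-case and multiple-imputation analyses (Protocol 13.4.3) and the SAP's per-protocol analysis are not primary.

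Two statements bear on how many patients are randomised. Protocol 4.1 says "We will be recruiting a total of 136 participants", and the SAP says the same. Protocol 11.3 says that patients who start the diet and withdraw "will be replaced if they do not reach Week 6 of the study including the EGD", and also that "Any enrolled participant will be included into any intent to treat analysis".

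**The concern.** A drop-out allowance that only enlarges the arms works when drop-outs disappear from the denominator: the remaining patients still show 45% and 70%. Under the plan's rule drop-outs stay in the denominator as non-remitters. With a fraction m missing in each arm, both rates are multiplied by (1 − m), and so is the difference. More patients do not restore that difference, and the number needed to offset it is larger than the usual inflation gives.

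Readers of 13.6 will take at least 80% power as describing the planned intention-to-treat comparison at about 15% drop-out. It does not. This matters most if the trial finds no significant difference between the diets, because that result would be judged against 80% power when about 70% may apply.

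**Working it through.** **Inputs.** From Protocol 13.6: 45% and 70%, two-sided α = 0.05, 60 then 68 per arm, likelihood-ratio test, about 15% drop-out. From 13.4.1 and the SAP: missing counts as failure. Assumed: 45% and 70% apply to patients with an endpoint, and missingness is equal in the arms. The 5% and 10% rates are scenarios; only 15% is in the document.

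**Method.** Exact binomial enumeration of the likelihood-ratio test (reject above 3.841), checked against the normal approximation

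z = [d√n − 1.96·√(2p̄(1 − p̄))] / √(p₁(1 − p₁) + p₂(1 − p₂)), power = Φ(z).

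**1. The plan's figure.** n = 60, 45% v 70%, d = 0.25, p̄ = 0.575: z = (1.9365 − 1.3702)/0.6764 = 0.837, power 79.9%; exact 80.6%. The starting point is right.

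**2. The allowance on its own terms.** 60/68 = 0.882, so 68 covers 11.8% loss. At 15% loss 0.85 × 68 = 57.8, about 58 remain, and power is 78.5%. Full cover needs 60/0.85 = 70.6, so 71. This is a small shortfall, and the text does say approximate.

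**3. The failure rule, 68 randomised per arm.** At 15% missing the rates are 0.85 × 45% = 38.25% and 0.85 × 70% = 59.5%; d = 0.2125, p̄ = 0.48875: z = (1.7523 − 1.3856)/0.6908 = 0.531, power 70.2%; exact 69.9%.

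| Missing per arm | Rates compared | Gap (points) | Exact power | Normal |
|---|---|---|---|---|
| 0% | 45% v 70% | 25 | 84.2% | 84.7% |
| 5% | 42.75% v 66.5% | 23.75 | 79.7% | 80.1% |
| 10% | 40.5% v 63.0% | 22.5 | 75.0% | 75.3% |
| 15% | 38.25% v 59.5% | 21.25 | 69.9% | 70.2% |

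By the normal approximation, 80% power needs 68, 77 and 86 per arm at 5%, 10% and 15% missing.

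**4. The part due to the failure rule alone.** At 11.8% missing: 80.6% if drop-outs leave, 73.2% if they count as failures, about 7 points. At 15%: 78.5% against 69.9%, between 8 and 9 points.

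**5. Replacement under 11.3 to 68 completers per arm.** At 15%, 68/0.85 = 80 randomised per arm, 160 in all. Power for 38.25% v 59.5% is 76.8% exact (77.2% normal).

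**6. Detectable difference, 68 per arm, 1FED 45%.** The difference among patients with an endpoint that gives 80% power is 25.1, 26.6 and 28.2 points at 5%, 10% and 15% missing. On the intention-to-treat scale the last is 28.2 × 0.85 = 24.0 points.

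**7. The table in 13.6.** Its rows vary n only, so no row reflects failure imputation. Two cells in the 50% column also miss 80% with nobody missing: n = 56 with 24 points gives 75.1%, and n = 60 with 23.5 points gives 76.4%. About 25.4 and 24.5 points are needed. By exact enumeration the other cells are within about half a point.

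**The case against.** The strongest objection is that 13.6 never says whether 45% and 70% are rates among patients with an endpoint or among all randomised. If they already count drop-outs as failures, 68 per arm gives about 84% and there is no shortfall. That stands as a condition. It is the less natural reading, because rates that already absorb drop-out would need no allowance.

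Second, 70% takes 136 as the number randomised, while 11.3 replaces early withdrawals. With 68 completers per arm the approximate figures are 82%, 80% and 77% at 5%, 10% and 15% missing (72, 76 and 80 randomised). This stands as the other end of the range; even so, 15% missing falls short of 80%.

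Third, drop-out is not the same as a missing endpoint. Protocol 9.4 includes biopsies at end of treatment or early withdrawal, and after early withdrawal "the end of treatment/early withdrawal visit should be conducted within one week" of stopping the diet. If half of a 15% drop-out had a usable biopsy, with the same remission rates, 7.5% would be missing and power at 68 per arm would be about 77%. So 15% missing is an upper case.

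Fourth, the primary test is a covariate-adjusted mixed model, which may recover power. For an assumed prognostic covariate with SD 0, 0.5 or 1.0 on the logit scale, simulated power at 15% missing is 71%, 73% and 78% at 68 per arm, and 78%, 80% and 84% at 80 per arm. Adjustment therefore recovers part of the shortfall or, under replacement, possibly all of it. The same adjustment gives 80%, 82% and 86% at 60 per arm with nobody missing, so the loss relative to that benchmark remains. These covariate strengths are assumptions, and the site effect was not simulated.

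Fifth, missingness may differ between diets. At 68 per arm, 10% missing on 1FED and 15% on 6FED gives about 60%; the reverse gives about 83%. Equal missingness is a convenience, not a worst case.

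**Conclusion.** The concern holds. The statement of at least 80% power does not describe the intention-to-treat test under the plan's own missing-data rule at the plan's own drop-out rate. For the unadjusted likelihood-ratio test of 13.6, power at 15% missing is about 70% with 136 randomised and about 77% with 136 completers. With 136 randomised, about 80% is kept only up to about 5% missing. These figures rest on 45% and 70% being rates among patients with an endpoint and on equal missingness. The two table errors are separate and smaller. The point should be fixed: it misstates what the trial can detect, but it does not invalidate the analysis.

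**What to change.** Keep the analysis as planned and rewrite the allowance in 13.6, for example:

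> Patients without a determinable endpoint count as failures. With 68 randomised per arm, power for 45% versus 70% among patients with an endpoint is about 80%, 75% and 70% if 5%, 10% and 15% per arm have no endpoint. At 15%, 80% power corresponds to a difference of about 28 points among them, or about 24 points in the intention-to-treat population.

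Then:

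- If 45% and 70% are meant as intention-to-treat rates, say so and state about 84% at 68 per arm instead.
- State whether 136 is the number randomised or the completer target under 11.3. If it is the latter, give about 77% at 15% missing and carry the randomised total (about 160) through the synopsis, Protocol 4.1 and the SAP.
- For a table that describes the intention-to-treat test, fix n at 68 and use missing rates as rows: about 25, 27 and 28 points at 5%, 10% and 15% for a 1FED rate of 45%. If the present table stays, correct its 50% column to about 25.4 points at n = 56 and 24.5 at n = 60.
- A sentence on whether an early-withdrawal biopsy can serve as the endpoint would help the reader choose the applicable missing rate.

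The cost is text and table edits, with no patients beyond those 11.3 already implies. The stated power becomes less favourable.

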4.6 Stratification, Randomization, and Blinding/Masking

All eligible participants will be randomized 1:1 to either the 1FED or 6FED. Following this six week phase 1, all patients will undergo EGD with biopsy, and those whose disease remains active may choose to move on to Phase 2 (to either 6FED or treatment with swallowed SGC). The sponsor, investigator, study staff, and participant will all have knowledge of the treatment being received.

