We will be recruiting a total of 136 participants, between the ages of 18-60. Participants will be enrolled in this study based on the presence of active eosinophilic esophagitis and adherence to the inclusion and exclusion criteria. We intend to conduct a prospective non-blinded randomized trial that compares a 1-food elimination diet (1FED) versus a 6-food elimination diet (6FED) for six weeks (Phase 1). Subsequently, non-responders to 1FED dietary elimination therapy will be treated with 6FED and non-responders to 6FED will be treated with SGC (swallowed fluticasone at a dose of 880 mcg twice a day) for six weeks (Phase 2) while on an unrestricted diet, if the participant chooses to continue in to Phase 2. The empiric dietary therapy interventions are as follows: 1-food elimination diet (1FED)—avoidance of milk vs. 6-food elimination diet (6FED)—avoidance of milk, egg, wheat, soy, fish/shellfish, and peanut/tree nuts, for six weeks. Milk elimination for both 1FED and 6FED includes all mammal milk (i.e. goat, sheep, and cow's milk must all be eliminated). The study design is shown schematically in Figure 1 Study Design Flowchart.

In Phase 1, participants will be randomized 1:1 to either 1 food elimination (milk elimination alone, 1FED) or 6 food elimination (milk, egg, wheat, soy, fish/shellfish, peanut/tree nuts elimination, 6FED) therapeutic diet. At the end of this phase, an EGD will be performed to assess remission. Attainment of remission (esophageal eosinophil counts <15 eosinophils/high powered field) after Phase 1 will result in study discontinuation and maintenance of the “successful” dietary therapy. Treatment non-responders may choose whether or not to continue into Phase 2. Dietary therapy non-responders who were on 6FED in Phase 1 and continue on to Phase 2 will receive topical swallowed steroids for six weeks (Phase 2) followed by EGD with esophageal biopsies. These participants will return to an unrestricted diet (i.e. stop 6FED) prior to beginning topical swallowed steroid therapy. Dietary non-responders in Phase 1 who were on 1FED and continue on to Phase 2 will continue to a 6FED

[figure not shown]
Version 10/14/2019

therapeutic diet (Phase 2) for six weeks followed by EGD with esophageal biopsies to assess remission.

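### Section 13.6 presents 68 per group as covering about 15% drop-out, but on its own evaluable-patient basis, before any replacement, 68 covers about 12%

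*Protocol*

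**What the plan says.** Protocol section 13.6 assumes remission of 45% on 1FED and 70% on 6FED, with a two-sided 0.05 test. It gives the base size as "A sample size of 60 patients per group (120 total patients) will provide at least 80% power" and names the method: "This calculation is based on a likelihood ratio test statistic for comparing proportions". The inflation follows: "To allow for a potential approximate 15% drop-out, the sample size will be increased to 68 patients per group", which makes 136 in total. A table then gives the difference detectable with 80% power at 56, 60, 64 and 68 per group. It is presented as showing robustness to different response and drop-out rates. At a 1FED rate of 45%, it lists 26 points for 56 per group and 25 points for 60.

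Three other places bear on how drop-out acts:

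- Protocol section 11.3 replaces participants who start the initial diet and withdraw before completing Week 6, including the endoscopy.
- Protocol section 13.4.1 puts every randomized patient in the primary analysis and counts an undetermined endpoint as treatment failure.
- The SAP, under Analysis Populations, keeps the failure rule. It removes only patients who were randomized inappropriately and never completed the enrollment visit, and it adds a per-protocol analysis.

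The SAP repeats the total ("We will be recruiting a total of 136 participants, between the ages of 18-60") but gives no drop-out rate or inflation step of its own.

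**The concern.** A reader takes section 13.6 to mean that 15% of patients can be lost with 60 per group, and hence 80% power, still in hand. The three figures 60, 15% and 68 do not fit together under either usual inflation rule. The section treats drop-out as a loss of patients: it adds patients to offset it, and apart from the response rate its table varies only the number per group. On that basis 68 is 3 per group short of what 15% requires. What is at stake is whether the drop-out tolerance given for the primary endpoint can be relied on, for example when recruitment or retention is judged against it.

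**Working it through.** **Inputs.** All are from Protocol section 13.6 except the 1:1 allocation, which is in section 4.6: remission 45% and 70%, two-sided alpha 0.05, likelihood-ratio test, 60 per group before inflation, 68 after, drop-out about 15%.

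**1. Does 60 reproduce?** Yes. Enumerating both binomial distributions for the two-sample likelihood-ratio test at 60 per group gives power 80.6%. The pooled normal approximation gives 79.9%. The base figure is sound, so the mismatch lies in the inflation step.

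**2. Inflation for 15% loss.** The size needed is n/(1 − d) = 60/0.85 = 70.6, so 71 per group (142 in total). The common shortcut n × (1 + d) = 60 × 1.15 gives 69. Neither gives 68.

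**3. What 68 covers.** The largest loss that leaves 60 is 1 − 60/68 = 8/68 = 11.8%.

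**4. What 15% loss leaves.** 68 × 0.85 = 57.8, about 58 per group, if nobody is replaced.

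**5. Power on an evaluable-patient basis, 45% versus 70%:**

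| Per group | Exact likelihood ratio | Pooled normal |
|---|---|---|
| 57 | 77.4% | 77.8% |
| 58 | 78.5% | 78.5% |
| 60 | 80.6% | 79.9% |
| 68 | 84.2% | 84.7% |
| 71 | 86.4% | 86.2% |

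Going from 60 to 58 costs 80.6 − 78.5 = 2.1 points by exact enumeration and 79.9 − 78.5 = 1.4 points by the normal approximation.

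**6. The protocol's table as loss from 68.** The rows 56, 60, 64 and 68 correspond to losses of 12/68 = 17.6%, 8/68 = 11.8%, 4/68 = 5.9% and 0%. The row that carries the 25-point claim is therefore the 11.8% scenario. No row represents 15%.

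**7. The planned primary analysis, where n stays at 68 and missing counts as failure.** The documents do not say whether 45% and 70% are rates among completers or already count drop-outs as failures, so both readings are shown.

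- *Completer rates, with 15% loss in each arm and no replacement (my assumption).* The rates become 0.45 × 0.85 = 38.25% and 0.70 × 0.85 = 59.5%. Power at 68 per group is 69.9% (exact) or 70.2% (normal). At 71 it is 73.2% or 72.1%, so the larger size would not restore 80%.
- *Rates that already count drop-outs as failures.* Power at 68 is 84.2% (exact), and no inflation was needed.

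**The case against.** The strongest reply is that the shortfall may never arise. A reader might infer from step 4 that the trial will finish with fewer than 60 evaluable per group. The documents do not support that. Section 11.3 replaces participants who start the diet and miss the Week 6 endoscopy, which is the main way an evaluable endpoint is lost. A fall below 60 would need replacement to fail, or losses that section 11.3 does not reach, such as patients randomized who never start the diet, or endoscopies whose biopsies cannot be read. This reply stands against the stronger reading. It does not make 68 a 15% allowance, because section 13.6 does not mention replacement.

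A second reply is that drop-outs do not leave the primary analysis at all. This is also correct. The evaluable-patient basis is inferred from how section 13.6 inflates and tabulates; it is not a rule for the primary analysis. It follows that 78% is not the power of the planned primary test. Neither reading in step 7 makes 68 the right inflation of 60 for 15%.

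A third reply is that the text says approximately 15%, that at least 80% power is attached to 60 per group and not to 68 after losses, and that the table already shows a harsher case at 56 per group for one extra point of detectable difference. This limits the weight of the point. Even so, the tolerance that 68 gives is nearer 12% than 15%, and the sentence can say so.

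**Conclusion.** The point holds as a small arithmetic inconsistency in section 13.6. On that section's evaluable-patient basis, and before any replacement, 68 per group tolerates 11.8% drop-out. A 15% allowance needs 71, a gap of 3 per group or 6 in total. At 15% loss about 58 per group remain, with power about 78% where section 13.6 claims at least 80% at 60.

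This rests on the stated 45% and 70%, equal loss in both arms and no replacement. It does not establish that the trial will miss 60 evaluable patients per group or that 136 is inadequate. Nor does it give the power of the primary analysis, which is about 70% or about 84% at 68 per group under the two readings in step 7.

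**What to change.** Keep 136 and restate the one sentence in Protocol section 13.6, for example: *68 per group allows for about 12% drop-out (60 evaluable per group), before any replacement under section 11.3.*

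If the sponsor also wants to report power at 15% loss, give two separate statements:

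- On the evaluable-patient (complete-case) analysis, about 58 per group remain without replacement, and power is about 78% for 45% versus 70%.
- On the primary analysis (all randomized, missing counted as failure), power at 68 per group is about 70% if 45% and 70% are completer rates with 15% loss per arm and no replacement, or about 84% if those rates already count drop-outs as failures. The sponsor should say which meaning was intended.

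The SAP needs no change on this point, since it only repeats the total. The cost is one sentence, or a short paragraph if the power statements are added. No patient number, test or decision rule changes; the stated drop-out tolerance becomes slightly less favourable.

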13.3 Measures to Minimize Bias

Patients will be randomized using a 1:1 scheme to 1FED or 6FED within each investigative site. Study staff will remain blinded to the randomization plan so they do not know the upcoming treatment assignment will be for a patient until after the patient has been assigned. Study personnel who will perform the histologic assessments will be blinded to treatment assignment for the slides they are evaluating. The CRPC will not be told which diet a

participant has been assigned to, and they will not receive any information or documentation indicative of dietary assignment. The slides and/or images of slides provided to the CRPC will not contain any information that reveals which diet the participant is on. Knowledge of dietary assignment will be limited to study staff who need to know which diet a participant has been assigned to (i.e. dietitians).

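### Two cells of the Section 13.6 power table fall short of their stated 80%, and its smaller-n rows do not represent drop-out in the primary analysis

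*Protocol*

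**What the plan says.** Protocol Section 13.6 sizes the trial on histologic remission at the end of Phase 1, with 45% assumed on 1FED and 70% on 6FED. It gives 60 per group for at least 80% power at two-sided 0.05, raised to 68 per group for approximately 15% drop-out. On method it states: "This calculation is based on a likelihood ratio test statistic for comparing proportions".

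It then introduces a table: "The following table displays the robustness of the sample size under various response rate and drop-out rate scenarios". The rows are 56, 60, 64 and 68 per group. The columns are 1FED rates of 45%, 50% and 55%, and each is headed as the difference detectable with 80% power. The middle column ("Difference to detect with 80% power if 1FED rate is 50" per cent) reads 24, 23.5, 23 and 23 points. No row or column carries a drop-out rate.

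Four other places bear on drop-out:

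- Protocol Section 13.4.1 includes all randomised patients in the primary analysis and imputes an undeterminable remission status as treatment failure. The SAP, under Analysis Populations, keeps the failure rule. It excludes only patients inappropriately randomised who never completed the enrolment visit.
- Protocol Section 11.3 replaces participants who do not reach Week 6 with its EGD, but keeps every enrolled participant in any intent-to-treat analysis.
- Protocol Section 13.4.3 plans a complete-case sensitivity analysis, and the SAP plans per-protocol analyses.
- Protocol Section 9.4 schedules biopsies at the early-withdrawal visit.

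**The concern.** The table is the only place in either document where the design is tested against departures from its assumptions; the SAP repeats the total of 136 but has no power section. A reader asking what happens if milk elimination does better than 45% would go to the 50% column. In the 56 and 60 rows that column matches the 55% column exactly, although at these rates the detectable difference should shrink as the 1FED rate rises. That prompted a recalculation.

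The drop-out label raises a different question. A row with fewer patients shows the effect of drop-out only if patients who drop out leave the denominator. In the primary analysis they stay in and count as failures, which lowers both remission rates and the gap between them. A reader who takes the smaller-n rows as drop-out scenarios would think the primary analysis better protected than it is.

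**Working it through.** **Inputs.** Two-sided alpha 0.05, 1:1 allocation, the likelihood-ratio test, the base-case rates and the table entries come from Protocol Sections 13.3 and 13.6. The failure rule comes from Section 13.4.1.

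**Methods.** (a) Enumeration of the named test: for every pair of remission counts (x, y) with n per group, compute G = 2 Σ O ln(O/E) over the four cells of the 2×2 table, and sum the two binomial probabilities over all pairs with G > 3.841. (b) As a check by hand, the pooled normal approximation, with d = p2 − p1 and p̄ the mean of the two rates:

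power = Φ{ [d√n − 1.96 √(2p̄(1−p̄))] / √(p1(1−p1) + p2(1−p2)) }

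**Step 1: the plan's own figure.** n = 60, 45% against 70%, p̄ = 0.575:
(0.25√60 − 1.96 × 0.6991) / 0.6764 = (1.9365 − 1.3702) / 0.6764 = 0.837, giving 79.9%. Enumeration gives 80.6%. The base case reproduces.

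**Step 2: the two cells.**
- n = 56, 50% against 74%, p̄ = 0.62: (1.7960 − 1.3454) / 0.6651 = 0.677, giving 75.1%. Enumeration: 75.1%.
- n = 60, 50% against 73.5%, p̄ = 0.6175: (1.8203 − 1.3471) / 0.6669 = 0.710, giving 76.1%. Enumeration: 76.4%.

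The unpooled normal approximation, the most favourable two-sided variant tried, gives 77.0% and 77.9%. A one-sided test gives about 84% and 85%, so sidedness does not explain the entries either.

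**Step 3: difference needed for 80% power, all cells, by enumeration (printed entry in brackets, in points).**

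| n per group | 1FED 45% | 1FED 50% | 1FED 55% |
|---|---|---|---|
| 56 | 26.07 (26) | **25.31 (24)** | 24.36 (24) |
| 60 | 24.82 (25) | **24.48 (23.5)** | 23.65 (23.5) |
| 64 | 23.98 (24) | 23.45 (23) | 22.96 (23) |
| 68 | 23.74 (24) | 23.17 (23) | 22.32 (22) |

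The two cells in bold are low by about 1.3 and 1.0 points. The others match to the nearest whole point, or to the nearest half point in the 60 row.

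**Step 4: drop-out under the failure rule.** With a proportion q of each arm undetermined and counted as failures, the analysed rates are 0.45(1−q) and 0.70(1−q), the difference is 0.25(1−q), and n stays at 68.

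| q | 1FED | 6FED | Difference | Power (normal approximation) |
|---|---|---|---|---|
| 5% | 42.75% | 66.5% | 23.75 | about 80% |
| 10% | 40.5% | 63.0% | 22.5 | about 75% |
| 15% | 38.25% | 59.5% | 21.25 | about 70% |

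For q = 15%, p̄ = 0.48875: (0.2125√68 − 1.96 × 0.7069) / 0.6908 = (1.7523 − 1.3856) / 0.6908 = 0.531, giving 70.2%. Enumeration agrees with these rounded figures.

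**The case against.** **The cells are illustrative.** The sample size rests on the 45% column, which reproduces, and the row at the enrolled size of 68 agrees with the test in all three columns. The two errors are about 1.0 and 1.3 points, and they change no test, alpha level or decision rule. All of this stands and limits the point to a correction.

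**A reader might infer that the whole 50% column, or the 55% column too, is wrong.** The documents do not support that. The 64-per-group cell at 50% is borderline: power is 78.4% by enumeration and 76.9% by the normal approximation. The enumerated difference of 23.45 still rounds to the printed 23. The 55% column is within rounding throughout.

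**A reader might also infer a copied column, since 50% and 55% agree in three of four rows.** At 64 per group, 23.45 and 22.96 both round to 23, so agreement there is legitimate. At 56 and 60 copying is possible, but nothing in the documents confirms it.

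**On drop-out, smaller n is right for some analyses.** It describes the complete-case and per-protocol analyses. Replacement under Section 11.3 would also recover some power, and some early withdrawals will have biopsies under Section 9.4 and so a determined outcome. These are fair qualifications. They do not rescue the label for the primary analysis, because replaced participants remain in the intent-to-treat set and the table models none of this. As an illustration, suppose replacement continued until 68 per arm had a Week 6 EGD, with 15% drop-out throughout. Then 68/0.85 = 80 per arm would be randomised, and the same formula gives (0.2125√80 − 1.3856) / 0.6908 = 0.746, or about 77%.

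**Conclusion.** Two of the twelve cells are wrong: at a 1FED rate of 50%, 56 per group with 24 points has about 75% power, and 60 per group with 23.5 points has about 76%. Reaching 80% takes about 25.3 and 24.5 points. The remaining cells and the base-case sample size agree with the named test to roughly the printed rounding.

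The drop-out description does not fit the primary analysis. For 45% against 70% with 68 per group, power is about 80%, 75% and 70% at 5%, 10% and 15% drop-out. This assumes equal drop-out in both arms, every drop-out undetermined, and no offset from replacement. All figures are for an unadjusted comparison of proportions, as in the protocol's own calculation, and not for the covariate-adjusted mixed model used in the primary analysis.

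A reader might conclude from the 70% figure that the trial is underpowered and the sample size must change. The documents do not establish that: the number of undetermined outcomes is unknown, some withdrawals will have biopsies, and replacement offsets part of the loss. What is shown is that the table does not demonstrate the drop-out robustness claimed for it.

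**What to change.** In the 50% column, change the entry for 56 per group to about 25.3 points and the entry for 60 per group to about 24.5. Leave the other ten cells as they are.

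Add drop-out rows with n fixed at 68 and drop-outs counted as failures, giving power at 5%, 10% and 15%, and state the assumptions about equal drop-out and replacement. Label the rows below 68 as applying only to complete-case or per-protocol analyses.

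The cost is one software run and a revised table with a sentence of explanation. The published figures become slightly less favourable. No change to the sample size, test or procedures is needed to make this correction.
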